9.2.2 Visit schedule

Patients will be recruited into the study in the order of their clinical visits scheduled. First 7 consented and suitable patients will be recruited for each site on each day, or fewer if without enough patients. One study visit is planned for each patient. Clinical assessments will be performed as part of routine clinical practice. Some laboratory tests results prior to the study can be used as source data as specified below. All data required should be entered into the Electronic Data Capture (EDC) System only after each patient has consented to participation.

During the study visit, the following procedures will be performed:

- Signature of informed consent and recording of the date informed consent was given
- Determination of eligibility by checking the inclusion/exclusion criteria
- Collect the following information
 - Demographic information
 - Personal health history
 - Diabetes Mellitus history
 - Chronic Kidney Disease history
 - Anti-Hypertension therapy history
 - Lipid Lowering therapy history
 - Anti-Platelet therapy history
 - hypoglycaemic history
 - Family health history (e.g., diabetes, hypertension, and Chronic kidney diseases)
 - Lifestyle
 - Physical examination
 - body weight
 - height
 - waist circumference
 - Vital sign
 - blood pressure
 - heart rate
 - Laboratory tests
 - HbA_{1c}
 - Albuminuria
 - Urine WBC
 - Fasting plasma glucose (FPG), (examined within one month prior to the visit)
 - Serum creatinine (SCr), uric acid (UA), high density lipoprotein cholesterol (HDL-C), low density lipoprotein cholesterol (LDL-C), triglyceride (TG), total cholesterol (TC) (If examined within three months prior to the visit, record the result; if examined without three

months prior to visit, record the date of last examination and re-examine by investigator's judgment.)

All of the laboratory tests will be performed by local laboratory and will be required on the same day of visit. The laboratory tests performed prior to the visit which can be used as source data are specified above.

Albuminuria can be measured in a random spot urine sample, a 24-h urine sample, or a timed urine sample. The results of albuminuria measurement will be categorized as normal, micro- and macro-albuminuria based on the definition in [Table 1](#).

Table 1 Definition of Albuminuria

Urinary albumin excretion	Random spot urine	24-h urine	timed urine
	ACR (mg/g)	24h UAE (mg/24h)	UAE (µg/min)
Normal	<30	<30	<20

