9.7 DATA ANALYSIS

All the following analyses are exploratory in nature and the p-values provided by these analyses will only be nominal. Missing data will not be imputed. Details of all analyses will be provided in the statistical and epidemiological analysis plan (SEAP).

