5.1 Does the protocol describe how the study exposure is defined and measured? (e.g. operational details for defining and categorising exposure, measurement of dose and duration of drug exposure)				
5.2 Does the protocol address the validity of the exposure measurement? (e.g. precision, accuracy, use of validation sub-study)				
5.3 Is exposure classified according to time windows? (e.g. current user, former user, non-use)				
5.4 Is exposure classified based on biological mechanism of action and taking into account the pharmacokinetics and pharmacodynamics of the drug?				

Comments:

This is a cross-sectional non-interventional study based on newly collected data. All the analyses will be descriptive. We will not study the effects of drug exposure.

Section 6: Outcome definition and measurement	Yes	No	N/A	Section Number
6.1 Does the protocol specify the primary and secondary (if applicable) outcome(s) to be investigated?				9.3
6.2 Does the protocol describe how the outcomes are defined and measured?				9.3
6.3 Does the protocol address the validity of outcome measurement? (e.g. precision, accuracy, sensitivity, specificity, positive predictive value, prospective or retrospective ascertainment, use of validation sub-study)				9.3
6.4 Does the protocol describe specific endpoints relevant for Health Technology Assessment? (e.g. HRQoL, QALYs, DALYS, health care services utilisation, burden of disease, disease management)				

Comments:

This Non-interventional study is a New Data Collection study of the T2DM of Old patient. There is not any Health Technology Assessment collected and the study outcomes are not relevant for Health Technology Assessment.

Section 7: Bias	Yes	No	N/A	Section Number

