5. OUTCOMES

5.1 MAIN OUTCOMES

The primary outcome is the proportion of patients attaining blood glucose control target of HbA1c<7%.

NSP 9.3.2 defines the following parameters as secondary outcomes:

- Renal function level of patients
- Treatment regimens for T2DM that patient are currently taking
- Proportion of macro-vascular and micro-vascular diabetic complications
- Proportion of Hypoglycaemic occurrence
- Proportion of Hypoglycaemia leading to therapy change
- Proportion of Anti-hypertension therapy usage
- Proportion of Lipid Lowering therapy usage
- Proportion of Anti-Platelet therapy usage
- Treatment adherence to Chinese T2DM guideline 2013

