6.3 PATIENT SETS ANALYSED

- Full Analysis Set – Eligible (FAS – E):
The FAS – E includes all eligible patients regarding to inclusion and exclusion criteria with an HbA1c measurement.
- FAS – Albuminuria:
The FAS – Albuminuria dataset is a subset of patients of FAS – E, which includes T2DM patients with albuminuria (micro-albuminuria without urinary tract infection based on urine WBC result and macro-albuminuria).
- FAS – E with Hypoglycaemia:
The FAS – E with Hypoglycaemia dataset is a subset of patients of FAS – E, which includes T2DM patients with Hypoglycaemia as medical history.
- FAS – E with Hypoglycaemia leading to therapy change:
The FAS – E with Hypoglycaemia leading to therapy change dataset is a subset of patients of FAS – E, which includes T2DM patients with Hypoglycaemia leading to therapy change as medical history.

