6.5 HANDLING OF MISSING DATA AND OUTLIERS

If patients have missing values for an outcome, those patients will be excluded for that outcome's analysis. No imputation approach will be applied. Any removal from the analysis will be documented.

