7. PLANNED ANALYSIS

The following standard descriptive statistical parameters will be displayed in summary tables of all continuous variables:

N	number of non-missing observations
Mean	arithmetic mean
SD	standard deviation
Min	minimum
Median	median
Max	maximum

Tabulations of frequencies for categorical data will include all possible categories and will display the number of observations in a category as well as the percentage (%) relative to the respective treatment group (unless otherwise specified, all subjects in the respective subject set whether they have non-missing values or not). Percentages will be rounded to one decimal place. The category missing will be displayed only if there are actually missing values.

For logistic regression model, adjusted odds ratio with 95% confidence interval, and p-value will be provided for the factors involved.

All data processing, summarization and analyses will be performed using Version 9.2 (or later) of the SAS statistical software package (Windows OS).

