7.6 MAIN ANALYSES

The blood glucose control proportion (HbA1c<7%) will be tabulated on FAS – E.

The analyses for parameters below will be performed on both FAS – E and FAS – Albuminuria:

- Renal function variables (eGFR, albuminuria, and CKD staging) will be summarized
- The proportion of the occurrence of hypoglycaemia and the proportion of hypoglycaemia leading to therapy change will be summarized descriptively.

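### Do the two hypoglycaemia proportions need a stated denominator and look-back period before they can be analysed?

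*SAP*

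**What the plan says.** Protocol 9.3.2 and SAP 5.1 list two hypoglycaemia outcomes by name only. One is occurrence; the other is "Proportion of Hypoglycaemia leading to therapy change". SAP 7.6 adds that "The proportion of the occurrence of hypoglycaemia and the proportion of hypoglycaemia leading to therapy change will be summarized descriptively", under a line that assigns these analyses to FAS – E and FAS – Albuminuria.

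Two general rules bear on the denominator:

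- SAP 6.5: "If patients have missing values for an outcome, those patients will be excluded" from the analysis of that outcome. There is no imputation, and removals are to be documented.
- SAP 7: unless something else is specified, percentages are relative to "all subjects in the respective subject set whether they have non-missing values or not". Counts are shown beside percentages, and a missing category appears when values are missing.

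On timing, Protocol 9.2.2 lists "hypoglycaemic history" among the items collected at the single visit. SAP 6.3 defines the hypoglycaemia subset as one "which includes T2DM patients with Hypoglycaemia as medical history" and defines the therapy-change subset in the same way. SAP 6.6 marks time windows as not applicable. SAP 3 says the two subsets were added for the treatment-pattern analysis, and SAP 7.2 uses them there.

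**The concern.** A patient who never had hypoglycaemia has no resulting therapy change to record. If the item is blank for such patients and the blank counts as missing, SAP 6.5 leaves only patients with hypoglycaemia in the denominator, while SAP 7 keeps everyone. The outcome's name can also be read as a share of those with hypoglycaemia. The same data could then give two therapy-change figures several-fold apart.

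Without a stated period, a reader might also not know whether the figures describe recent or lifetime experience. These proportions answer one of the six secondary objectives in Protocol 8. Protocol 9.7 promises that "Details of all analyses will be provided in the statistical and epidemiological analysis plan (SEAP"), so the SAP is where one would look for the definition.

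**Working it through.** **Set size.** The documents give no hypoglycaemia rate. Their only computed figure is the evaluable sample for the primary outcome (Protocol 9.5): 1.96² × 0.39 × 0.61 / 0.025² = 1462.2, rounded up to 1463, as stated. For recruitment, 1463 / 0.975 = 1500.5, against 1500 planned. N = 1463 is used below as the approximate size of FAS – E. All hypoglycaemia, therapy-change and missing-data rates below are assumptions.

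**Which denominator the text gives.** SAP 7.6 names the sets. SAP 7 takes percentages over the whole set by default. SAP 6.3 treats each hypoglycaemia condition as a history that a member of FAS – E either has or does not have. On that reading, a patient without hypoglycaemia is a no for both outcomes. An item that does not apply to a patient is not ordinarily a missing outcome value in the sense of SAP 6.5.

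**Size of the conflict when non-cases are coded no.** Let P be the proportion among patients with an answer (SAP 6.5) and m the share with no answer. SAP 7 gives P(1 − m), so the gap is P × m.

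| P (SAP 6.5) | m = 1% | m = 5% | m = 10% |
|---|---|---|---|
| 5% | 4.95% | 4.75% | 4.5% |
| 20% | 19.8% | 19.0% | 18.0% |
| 30% | 29.7% | 28.5% | 27.0% |

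For P of 5% to 20% the gap runs from 0.05 × 0.01 = 0.05 point to 0.20 × 0.10 = 2 points. At P = 30% with 10% missing it is 3 points. With nothing missing it is zero. Since SAP 6.5 documents removals and SAP 7 displays a missing category, m is visible either way and one figure converts to the other.

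**Size if the item is blank for non-cases and blank means missing.** Let H be the number with hypoglycaemia and C the number with therapy change. The readings are C/N and C/H, and their ratio is N/H = 1/p, where p = H/N. For p of 10%, 20%, 30% and 40% the ratio is 10, 5, 3.3 and 2.5. Example with p = 20% and 40% of those patients changing therapy: H = 293 and C = 117, giving 117/1463 = 8.0% (95% CI half-width 1.4 points) against 117/293 = 39.9% (half-width 5.6 points).

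**Can the reader recover both?** Yes. SAP 7 requires counts, so the tables show C, H and the set size, for FAS – E and for FAS – Albuminuria. In the example, a reader who sees 117 and 293 gets 39.9% by one division. For FAS – E, the treatment-pattern tables in SAP 7.2 also show both subset sizes.

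**Period.** Protocol 9.2.2 states windows where it wants them: one month for FPG, and three months for serum creatinine, uric acid and lipids. It states none for hypoglycaemic history, and SAP 6.6 sets none. The ordinary reading is ever-history. The distinction matters for interpretation. With a first-event rate of 5% a year shared by all patients over 10 years, 1 − exp(−0.5) = 39.3% ever against 1 − exp(−0.05) = 4.9% in 12 months, a ratio of 8.1 before rounding. If instead 20% of patients have 0.5 events a year and the rest none, 0.2 × (1 − exp(−5)) = 19.9% against 0.2 × (1 − exp(−0.5)) = 7.9%, a ratio of 2.5. That is a reason to label the table, but it does not show that the planned figure would be wrong.

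**The case for a change.** The best case for a change is that SAP 7.6 never says which general rule governs. The words *unless otherwise specified* in SAP 7 do not settle it: if SAP 6.5 is the exception, the default in SAP 7 would apply to no outcome with missing data. The hypoglycaemia subset exists but is assigned to treatment pattern, not named as a denominator. Annex 2, item 6.2 asks "Does the protocol describe how the outcomes are defined and measured" and points to section 9.3, where these two outcomes have names only. The SAP is the final version before database lock, and a clarification would take a few lines and need no new data.

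What stands is that sections 6.5 and 7 are in tension, the outcome name is loose, and no look-back period appears in the readable text. But the tension is general, affecting any outcome with missing values, and it is small unless the blank-item assumption holds. The eCRF, which would decide that, is not in the documents. SAP 5.2, 6.4, 7.5 and 7.7 are also absent from the public text, so a denominator or period may be given there. A ticked checklist box is not evidence of a faulty analysis. An added percentage column would be convenient, but it can be derived from output already planned.

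**Conclusion.** No change to the plan is needed. Read together, SAP 6.3, 7 and 7.6 lead to a usable analysis: both proportions over FAS – E or FAS – Albuminuria, patients without hypoglycaemia counted as no, and history taken as ever. Following that would not give a wrong result.

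On this reading, the two missing-data rules differ by about 0.1 to 2 points for 1% to 10% missing and a proportion of 5% to 20%, and by 3 points at 30% with 10% missing. The factors of 2.5 to 10 rest on an assumption about an unseen form; even then both percentages follow from the planned counts. The analyses are exploratory under Protocol 9.7, and no test depends on these figures. A table footnote giving the denominator, the number with unknown history and any recall period on the eCRF would be good reporting practice.

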7.8 EXPOSURE TIME

Not applicable.

7.9 SAFETY ANALYSIS

7.9.1 Adverse events

AEs will be summarized on both FAS – E and FAS – Albuminuria.

Unless otherwise specified, the analyses of AEs will be descriptive in nature. All analyses of AEs will be based on the number of subjects with AEs and NOT on the number of AEs.

An overall summary of adverse events will be presented.

Adverse events will be coded according to the most recent version of the Medical Dictionary for Regulatory Activities (MedDRA). The frequency of subjects with adverse events will be summarized by treatment, system organ class and preferred term. The system organ classes will be sorted in alphabet order, preferred terms will be sorted by frequency (within system organ class).

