9.3.2 Secondary outcomes

Secondary outcomes are:

- Renal function of patients

- Estimated glomerular filtration rate (eGFR) evaluated by CKD Epidemiology Collaboration (CKD-EPI) equation expressed as:
$$GFR = 141 \times \min(Scr/\kappa, 1)^\alpha \times \max(Scr/\kappa, 1)^{-1.209} \times 0.993^{Age} \times 1.018 \text{ [if female]} \times 1.159 \text{ [if black]}$$

If SCr is in mg/dL, $\kappa = 0.7$ if female, $\kappa = 0.9$ if male
If SCr is in $\mu\text{mol/L}$, $\kappa = 61.9$ if female, $\kappa = 79.6$ if male
 $\alpha = -0.329$ if female
 $\alpha = -0.411$ if male
min = the minimum of Scr/ κ or 1
max = the maximum of Scr/ κ or 1
- Albuminuria categorized as micro-albuminuria and macro-albuminuria according to the definition in [Table 1](#).
- Treatment regimens for T2DM that the patients are currently taking, categorized as follow: (GLP-1 has been regard as OAD even though it's an injection treatment)
 - No treatment
 - Only diet control and exercise
 - Oral antidiabetic drug (OAD)-Mono therapy
 - Biguanide
 - α -glucosidase inhibitor
 - Sulfonylureas
 - Thiazolidinediones
 - Meglitindes
 - Dipeptidyl peptidase-4 (DPP-4) inhibitors
 - Sodium-glucose co-transporter (SGLT-2) inhibitors
 - Glucagon like peptide-1 (GLP-1) analogue
 - OAD-Combined therapy
 - Dual
 - Triple
 - Insulin only
 - OAD + Insulin
- Proportion of macro-vascular and micro-vascular diabetic complications:
 - Cardiovascular disease (i.e., coronary artery disease)
 - Cerebrovascular disease (i.e., ischemic stroke)
 - Peripheral vascular disease (i.e., diabetic foot)
 - Kidney disease (i.e., diabetes nephropathy)
 - Retinopathy
 - Neuropathy
- Proportion of Hypoglycaemic occurrence
- Proportion of Hypoglycaemia leading to therapy change
- Proportion of Anti-hypertension therapy usage
- Proportion of Lipid Lowering therapy usage
- Proportion of Anti-Platelet therapy usage
- Treatment adherence to Chinese T2DM guideline 2013
 - 0-3 month
 - 3-6 month
 - 6-12 month
 - >12 month

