11.2 ADVERSE REACTION AND FATAL ADVERSE EVENT REPORTING

The investigator shall maintain and keep detailed records of all AEs in their patient files.

Collection of AEs

The study design is of non-interventional nature and the study is conducted within the conditions of the approved marketing authorisation. Sufficient data from controlled interventional trials are available to support the evidence on the safety and efficacy of the studied BI drug. For this reason the following AE collection and reporting requirements have been defined.

The following must be collected by the investigator in the (e)CRF from signing the informed consent onwards until the end of the study for any BI drug approved for the indication of T2DM

- all ADRs (serious and non-serious),
- all AEs with fatal outcome (death).

All ADRs, including those persisting after study completion must be followed up until they are resolved, have been sufficiently characterized, or no further information can be obtained.

The investigator carefully assesses whether an AE constitutes an ADR using the information below.

Causal relationship of adverse event

The definition of an adverse reaction implies at least a reasonable possibility of a causal relationship between a suspected medicinal product and an adverse event. An adverse reaction, in contrast to an adverse event, is characterized by the fact that a causal relationship between a medicinal product and an occurrence is suspected.

Medical judgment should be used to determine the relationship, considering all relevant factors, including pattern of reaction, temporal relationship, de-challenge or re-challenge, confounding factors such as concomitant medication, concomitant diseases and relevant history.

Arguments that may suggest a **reasonable causal relationship** could be:

- The event is **consistent with the known pharmacology** of the drug.
- The event is known to be caused by or **attributed to the drug class**.
- A **plausible time to onset of the event** relative to the time of drug exposure.
- Evidence that the **event is reproducible** when the drug is re-introduced.
- **No medically sound alternative etiologies** that could explain the event (e.g. preexisting or concomitant diseases, or co-medications).
- The event is typically **drug-related and infrequent in the general population** not exposed to drugs (e.g. Stevens-Johnson syndrome).

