The following must be reported by the investigator on the NIS AE form from signing the informed consent onwards until the end of the study:

Type of Report	Timeline
All Serious ADRs (SADRs) associated with the any BI drug approved for the indication of T2DM	immediately within 24 hours
All AEs with fatal outcome in patients exposed to any BI drug approved for the indication of T2DM	immediately within 24 hours

All non-serious ADRs associated with the any BI drug approved for the indication of T2DM	7 calendar days
All pregnancy monitoring forms concerning DEDP to any BI drug approved for the indication T2DM	7 calendar days

The same timelines apply if follow-up information becomes available for the respective events. In specific occasions the Investigator could inform the sponsor upfront via telephone. This does not replace the requirement to complete and fax the NIS AE form.

Information required

For each reportable adverse event, the investigator should provide the information requested on the appropriate (e)CRF pages and the NIS AE form.

Reporting of related Adverse Events associated with any other BI drug

The investigator is encouraged to report all adverse events related to any BI drug other than the BI drug approved for the indication of T2DM according to the local regulatory requirements for spontaneous AE reporting at the investigator's discretion by using the locally established routes and AE report forms. The term AE includes drug exposure during pregnancy, and, regardless of whether an AE occurred or not, any abuse, off-label use, misuse, medication error, occupational exposure, lack of effect, and unexpected benefit.

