5.3 OTHER VARIABLES

All adverse drug reactions (ADRs) (serious and non-serious) and all AEs with fatal outcome (death) for any BI drug approved for the indication of T2DM must be collected by the investigator from signing the informed consent onwards until the end of the study.

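### The safety tables in SAP 7.9.1 use analysis sets that do not match how events are collected: the overall percentage includes patients not taking the drugs concerned, and some consented patients are left out

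*SAP*

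**What the plan says.** **Tabulation.** SAP 7.9.1 states that "AEs will be summarized on both FAS – E and FAS – Albuminuria". The unit is the subject with an event, and an overall summary is planned. A further table is described: "The frequency of subjects with adverse events will be summarized by treatment, system organ class and preferred term". Under SAP 7, percentages in frequency tables are "relative to the respective treatment group (unless otherwise specified, all subjects in the respective subject set", whether or not values are missing.

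**Sets.** In SAP 6.3, FAS-E "includes all eligible patients regarding to inclusion and exclusion criteria with an HbA1c measurement". FAS-Albuminuria is a subset of FAS-E. The other two sets listed there are hypoglycaemia subsets of FAS-E. SAP 6.3 lists no set of all consented patients and no set of drug users.

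**Collection.** SAP 5.3 names ADRs and fatal AEs, which "for any BI drug approved for the indication of T2DM must be collected by the investigator". Protocol 11.2 gives the scope of eCRF collection as "from signing the informed consent onwards until the end of the study for any BI drug approved for the indication of T2DM". Its expedited-reporting table lists "All AEs with fatal outcome in patients exposed to any BI drug approved for the indication of T2DM". Protocol 9.3.4 names the same kinds of event and the same period, but does not mention BI drugs.

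**Population.** Protocol 9.2.1 takes consecutive older outpatients with T2DM and has no criterion on drug use. The regimen categories in protocol 9.3.2 include no treatment and "Only diet control and exercise".

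**The concern.** An event enters the numerator only if it is tied to a BI drug approved for T2DM. The denominator contains everyone in the set, including patients on no drug, on diet and exercise alone, or only on other products. Some of them could start such a drug after the visit, but until then nothing that happens to them is reportable. The label 'AEs' also suggests a wider collection than took place.

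A reader of the study report could take a percentage on FAS-E as how often patients on these drugs had a reaction or died. A low count would then look more reassuring than the data allow.

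A second mismatch is that collection starts at consent, while the tables require eligibility and an HbA1c. A reportable event in a consented patient who fails either condition would be in the database but not in the safety tables.

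**Working it through.** **1. Collection and tabulation side by side**

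| | Collected (protocol 11.2, SAP 5.3) | Tabulated (SAP 7.9.1, 6.3) |
|---|---|---|
| Events | ADRs and fatal AEs | 'AEs' |
| Drug condition | BI drugs approved for T2DM | None |
| Patients | From consent onward | Eligible and with an HbA1c; for FAS-Albuminuria, also with qualifying albuminuria |

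The columns differ in every row.

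**2. The plan's figures.** Protocol 9.5 assumes a proportion p = 0.39 and a two-sided 95% interval of total length L = 0.05.

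- n = z² × p × (1 − p) / (L/2)² = 3.8415 × 0.2379 / 0.000625 = 1462.2, rounded up to 1,463, as stated.
- 1,463 / 0.975 = 1500.5, against 1,500 stated.

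The expected size of FAS-E is therefore about 1,463, before any loss for ineligibility.

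**3. Patients left out for want of an HbA1c.** 1,500 − 1,463 = 37 (directly, 1,500 × 0.025 = 37.5). The documents give neither the number found ineligible nor the number of users among the 37.

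**4. Dilution, on the BI-only reading of protocol 11.2 and SAP 5.3.** Let N be the set size, f the share using a BI T2DM drug, and r the share of users with a reportable event.

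- Subjects with an event = N × f × r
- Overall percentage = (N × f × r) / N = f × r
- Frequency among users / overall percentage = 1/f

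The two agree only if f = 1, and no eligibility criterion requires that. The documents do not give f, so the following only illustrates the direction. Suppose 10 subjects have an event; the shares are assumed.

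| Assumed f | Users in FAS-E (1,463 × f) | 10 / 1,463 | 10 / users |
|---|---|---|---|
| 10% | 146.3 | 0.68% | 6.84% |
| 20% | 292.6 | 0.68% | 3.42% |
| 50% | 731.5 | 0.68% | 1.37% |

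**5. The protocol 9.3.4 reading.** With no BI restriction, reactions to other drugs and any death would also enter the numerator. The relation f × r then no longer holds. The overall percentage would still not be a frequency among users of BI drugs, but the size of the gap would no longer be 1/f.

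**The case against.** **The plan never calls this percentage a rate among exposed patients.** That is correct. SAP 7.9.1 describes the AE analyses as descriptive, protocol Annex 2 says the effects of drug exposure will not be studied, and SAP 6.1 and 7.8 mark exposure and exposure time as not applicable. Safety is not a primary or secondary outcome. This limits the weight of the point. It does not repair a table whose title and denominator do not fit what was collected.

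**A breakdown by treatment is planned, and the default denominator in SAP 7 is the treatment group.** If treatment means the regimens of protocol 9.3.2, patients on no drug would fall outside the drug groups. But those regimens are classes and combinations, not BI products. The phrase is attached to the table by system organ class and preferred term; it does not create a denominator of BI-drug users for the overall summary.

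**'By treatment' may be defined elsewhere.** A reader might infer that the SAP leaves it undefined. The supplied text does not support that: section numbers are skipped, and SAP 7.9.2 refers to a section 7.7 that is not in it. The absence of a safety set is firmer, because SAP 6.3 is supplied.

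**A percentage of users may be unobtainable and hard to interpret.** This stands in part. SAP 7.2 summarises coded medication by ATC level 4 and preferred term, and the documents do not show that BI products can be identified for each patient. With one visit and no exposure time, even a percentage of users would be hard to interpret as a risk. Counts are therefore the safer default.

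**Conclusion.** The point holds and is minor. Applied as written, SAP 7.9.1 gives an overall percentage that is diluted by non-users, and it can omit reportable events in consented patients outside FAS-E.

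Two stronger readings should be resisted:

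- A reader might infer a specific understatement, such as tenfold or twofold. The documents give no share of users, and the 1/f relation depends on the BI-only reading, which protocol 9.3.4 does not state. Only the direction is supported.
- A reader might infer that safety events go unreported. They do not: events in patients outside FAS-E are still collected in the eCRF and go through expedited reporting under protocol 11.2. They are missing only from the tables. Missing HbA1c accounts for about 37 of 1,500 patients on the plan's assumption; the number of ineligible patients is unknown.

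The conclusion assumes that collection follows protocol 11.2 and SAP 5.3, and that not every FAS-E patient takes a BI T2DM drug.

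**What to change.** 1. In SAP 6.3, add a safety set of all consented patients, with no HbA1c or eligibility condition.
2. In SAP 7.9.1, title the tables 'ADRs and fatal AEs for BI drugs approved for T2DM' and report counts on the safety set. Make any albuminuria split a subset of that set.
3. Give percentages among recorded users of a BI T2DM drug only if the medication data identify them. Otherwise give counts only, or percentages of all consented patients with a footnote that these are not rates among exposed patients. Changing to the all-consented denominator does not by itself remove the dilution.
4. If no other SAP section defines 'by treatment', state it as by BI drug or remove it.
5. Reconcile protocol 9.3.4 with protocol 11.2 and SAP 5.3 on whether collection is limited to BI T2DM drugs. The table title should follow the outcome.

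The cost is one set definition, a title, and a stated denominator or footnote. The fallback needs no new data, since SAP 7.9.5 already counts enrolled and entered subjects. Percentages among users depend on product-level medication data, whose availability the documents do not show.
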